2.7 EXPLORATORY HEALTHCARE UTILIZATION AND ECONOMIC ANALYSIS

This section provides a high-level summary of the Health Care Economics portion of this trial. The following text is taken from the Sponsor's summary. Please consult the standalone Health Care Economics Protocol for additional details of these analyses.

To assess resource use associated with chronic low back pain, participants will be run through a secure Datavant matching process to be linked to their healthcare claims data if it is available in the Komodo data set. The claims will provide descriptive characterizations of resource use and costs associated with chronic low back pain. For patient-level changes in resource use, and for comparisons between study arms, only the participants with complete claims files will be assessed. Claims-matched data will capture all interactions with the healthcare system that generate an insurance claim record, which includes such things as physician visits, interventions such as steroid injections, surgery or physical therapy, emergent use of services, medications, and diagnostic procedures. Claims adjudication often lags a few months, so the most robust analyses of utilization will be performed about 6 months after the time point of interest. Health economic modeling will be performed after 1 year to assess the cost and economic outcomes of the EaseVRx intervention.

The Komodo claims data provides a real-world source of utilization and cost parameters associated with claims of chronic low back pain. As such, it can be used more broadly to either compare the study participants' resource use and

costs to the broader population of patients with chronic low back pain, or a “synthetic arm” can be constructed using available demographic data to match any of the study arms.

2.8 SAMPLE SIZE

2.8.1 MULTIPLE PRIMARY ENDPOINT POWER ANALYSIS

Clinical trial simulation was used to derive the statistical operating characteristics of this trial (FDA Guidance 2010). These simulations provide calculations of Type I error, power, and sample sizes for the primary superiority study claim under the default reference assumptions and a range of sensitivity analyses to ensure the trial is conservatively designed.

There are many ways to generate simulated clinical trials for the use in statistical power calculations. Regardless of the method, the simulated data have no impact on the actual trial. For this trial, simulated datasets were generated by drawing from random bivariate normal distributions with specified means, SDs, and correlations between the two primary endpoints, Pain Intensity and Pain Interference. The model parameters (the mean, SD, and correlations) were based on the summary statistics taken from the previous EaseVRx trial to support the initial default assumptions.

Note, the previous trial measured interference in four domains from the DoD/VA Pain Scale, Sleep, Mood, Activity, and Stress. The future trial will collect these measurements as an average of 7 domains through the BPI survey. For sample size estimation, the average of the 4 DoD/VA Pain Scale domains collected in the previous trial will be used as an estimate for the BPI survey. As will be discussed below, the sample size calculations have been appropriately made more conservative to deal with possible differences arising from the surveys.

Unadjusted results from the previous trial are shown in the following table.

Table 2: Previous Trial Results for Power Analysis

	EaseVRx						Sham					
		Intensity		Interference*		Cor		Intensity		Interference*		Cor
		N	Mean	SD	Mean	SD		N	Mean	SD	Mean	SD
Baseline (BL)**	94	5.10	1.24	4.78	1.91	0.72	94	5.24	1.14	5.08	1.64	0.71
Week 8 (W8)	84	2.98	1.90	2.26	2.13	0.81	84	3.95	2.03	3.24	2.31	0.85
Change (BL to W8)	84	-2.12	1.64	-2.56	1.99	0.76	84	-1.21	1.68	-1.82	1.97	0.77

*Calculated as mean of Mood, Activity, Stress and Sleep.
** Refers to data collected at relative day -7, which is the average of 3 timepoints between -14 and 0 days before first treatment.

This table shows that the mean changes for Pain Intensity are -0.91 higher for EaseVRx, and the mean change for Pain Interference is -0.74 higher for EaseVRx.

Using the observed data in the previous trial and shown in the table immediately following this paragraph, clinical trial simulation was used to generate thousands of future trials where the group level summary statistics (means, SDs and correlation between endpoints) matched observed data. For every trial, two sample t-tests were performed and statistics from each recorded. Multiplicity adjustment was applied to each of the p-values (testing the group difference < 0). Each trial matrix was discretized into either success or failure with every trial being assumed a success if either p-value was less than 0.025. The binary trial success from 10,000 trials was stored, and the fraction of all simulated trials equal to the trial's power.

In this framework, the previously observed data is used in the assumptions. It is assumed that the difference observed in the last trial is clinically meaningful and worth detecting. That is, is the group difference in Intensity of -0.91 (EaseVRx= -2.12 vs. ShamVR= -1.21) and Interference of -0.74 (EaseVRX= -2.56 vs. ShamVR=-1.82) clinically meaningful and worth studying. The current design assumes that it is worth detecting.

Note that the assumed correlation at 0.76 and 0.77 does not significantly impact the total sample size in this study and is generally understood to be conservative. If the endpoints were entirely not correlated, power would go up. When the endpoints are assumed to be perfectly correlated, power drops, but only ~1.5%.

Before LTF and Matching adjustment, with 240 total subjects (120 and 120 in the 1:1 randomization) provide >95.0% power to detect either an improvement in Intensity or Interference with a two-sample t-test testing the difference in means is less than 0 for the

week 8 change value. The p-values are adjusted for multiplicity using a Hochberg correction. Study success is defined and will be declared if either p-value is < 0.025 .

The trial size of $N= 240$ does not include adjustment for LTF or the expected match rate. When the Claims match rate is only 50% and Lost to Follow-up is 15%, the study sample size is $N= 565$. When the match rate is 33% and Lost to Follow-up is 15%, the study sample size is $N= 855$.

- $240 / .500 = 480$ accounting for 50% matching only
- $480 / .850 = \sim 565$ accounting for 50% matching + LTF
- $240 / .330 = \sim 730$ accounting for 33% matching only
- $730 / .850 = \sim 855$ accounting for 33% matching + LTF

The sample size is further increased to allow for testing of the secondary endpoint of 30% improvement in either Pain Interference or Intensity at longer time points. As this study extends to 24 months' follow up, the Lost to Follow-up rate for the secondary endpoints may exceed 15%. Given these two factors (less power 30% responder analysis and possible additional LTF), the trial may enroll up to 145 subjects beyond the minimum sample size for a total study size of $N= 1000$.

2.8.2 COMMENT ON STATISTICAL POWER IN THIS TRIAL

- It is noted that this trial is statistically powered with 240 subjects before adjusting for Lost to Follow-up or adjustment for matching. Therefore, this trial may detect differences that are small and therefore not meaningful for any individual patient. To prospectively guard against capitalizing on differences not necessarily important to patients, a set of responder analysis are specified so that proportional differences between the groups will be provided such that each subject will only contribute "success" when they have individually achieved a meaningful improvement.

2.9 HANDLING OF MISSING DATA AND SPECIFICATION OF THE ESTIMAND

Primary effectiveness data may be unavailable for several reasons. This section describes the implications and handling of unavailable primary outcome data on the estimand of interest. For this study, the estimates of interest are the group mean differences in changes from baseline to 8 weeks in Pain Intensity and Pain Interference had subjects completed 8 weeks of follow-up and not withdrawing for lack of treatment effectiveness.

The long term estimands of interest are the change in Pain Interference and Pain Intensity at 4 weeks post treatment, 8 weeks post treatment, 12 weeks post treatment, 6 months post treatment, 12 months post treatment, 18 months post treatment and 24 months post treatment.

2.9.1 HANDLING DATA FOLLOWING SUBJECT WITHDRAWAL DUE TO LACK OF TREATMENT EFFECTIVENESS

Discontinuation due to lack of treatment effectiveness may occur. This discontinuation is an “intercurrent event” in the sense of Draft Guidance E9(R1). “[I]ntercurrent events such as discontinuation or switching of treatment, or use of rescue medication, may in some circumstances render the later measurements of the variable irrelevant or difficult to interpret even when it can be collected.” It is necessary to specify how data from subjects with intercurrent events will be handled to provide specificity about the estimand.

E9(R1) discusses several approaches to handling data after an intercurrent event. One suggested approach is to incorporate the intercurrent event as a failure mode in a composite endpoint requiring clinically meaningful improvements. However, if the primary effectiveness endpoints are continuous changes from baseline rather than a responder analysis, another approach is necessary.

Another approach to handling intercurrent events is to adopt a “treatment policy” estimand. This approach requires data collection after the intercurrent event. If data is not collected after the intercurrent event, it is not possible to adopt a “treatment policy” estimand. Moreover, the treatment policy estimate does not directly pertain to the effectiveness of the investigational device, but rather pertains to the comparison of starting off with the investigational device and starting off with the control device but allowing changes to the treatment regimen as deemed medically necessary. The treatment policy approach is not consistent with the estimand defined above. Adopting the treatment policy approach changes the primary question the study is designed to address.

The hypothetical approach is “envisaged in which the intercurrent event would not occur: the value to reflect that scientific question of interest is that which the variable would have taken in the hypothetical scenario defined.” That is, the “treatment effect of interest might concern the outcome if the subsequent active treatment had not been administered.”

The hypothetical approach is consistent with the estimand defined above and so will be used for this study. It is reasonably assumed that subjects who discontinue due to lack of effectiveness do not experience clinically significant improvement in pain. Therefore, to include these subjects in the primary analysis, a baseline carried forward approach will be used implying that subjects who discontinue due to lack of effectiveness are given a value of zero for their changes from baseline. A sensitivity analysis will be performed in which these subjects are given the last observation prior to the discontinuation as their Primary endpoint (week 8) value.

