2.4 TESTING THE PRIMARY SUPERIORITY HYPOTHESIS

Superiority testing will be performed using a mixed model for repeated measures (MMRM) analysis of covariance (ANCOVA) Model. The MMRM approach is a direct likelihood

approach requiring specialized statistical software. For this study, all MMRM parameters will be estimated using appropriate statistical software (see Software below). The MMRM model is notable for its inclusion of all available data from all eligible subjects and does not require their exclusion as in complete case analysis or arbitrary assignment of some value as in Last Observation Carried Forward (LOCF). Inclusion of outcome data from time points earlier than Week 8 informs the implicit imputation of missing Week 8 values through the covariance matrix used to model the random effects.

The random effects in an MMRM model are based on the so-called ‘unstructured covariance matrix’ in which variances over time are allowed to vary as are the pair-wise correlations over time.

The values over time include all Pain scores, namely at each and all of the 2x week follow-up time points through Week 8.

All Pain values will be included in the analysis even if they are obtained out-of-window. The fraction of out-of-window visits will be summarized at each time point.

The contrast indicated by the primary hypotheses above, $\delta(\text{pain})_{\text{EaseVRx}} - \delta(\text{pain})_{\text{sham}}$ will be estimated as the treatment group contrast from baseline to Week 8 in the Pain score derived from the MMRM. The null hypothesis is that the true value of this contrast is equal to zero. The same approach will be taken for testing both Pain Interference and Pain Intensity.

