2.4.2 DETAILS OF THE MMRM

As stated above, the covariance matrix for MMRM is an unstructured covariance matrix in which each of the variances (at every follow-up) are free to vary as are the covariances.

That is, the covariance matrix for the MMRM will not include any random effects per se, but accounts for correlations among errors by specifying the form of the covariance matrix. The MMRM employs an unstructured covariance to produce inferences that are valid under the so-called ‘missing at random’ (MAR) assumption which is more generally true than the ‘missing completely at random’ assumption that is required for validity of analyses restricted to complete cases.

The longitudinal model will be specified as a repeated measures model that expresses the Pain score as a linear function of treatment, time, treatment-by-time interaction, and a covariate of the baseline pain measurement.

The model is mathematically expressed as:

$$\mathbf{Y}_i = \mathbf{X}_i \boldsymbol{\beta} + \mathbf{e}_i$$

Where:

- \mathbf{Y}_i is change from baseline to Week 8 in Pain
- $\boldsymbol{\beta}$ is a vector of fixed-effect regression parameters which includes:
 - o μ , the overall mean
 - o θ , the treatment effect
 - o τ , a vector of post-baseline time effects
 - o η , a vector of treatment-by-time interaction effects
 - o ϕ , a vector of covariate effect parameters that only includes baseline Pain score but in general could include additional baseline variable
- \mathbf{X} is a design matrix for the fixed effects, and
- \mathbf{e} is the error vector with
 - o $E(\mathbf{e}) = \mathbf{0}$ and
 - o $Var(\mathbf{e}) = \sigma_e^2 V_{unstructured}$

The specific model to be used may be expressed as:

$$\mathbf{Y} = \mathbf{b}_{int} + \mathbf{b}_{base} + \mathbf{b}_T + \mathbf{b}_1 + \dots + \mathbf{b}_{56} + \mathbf{b}_T \mathbf{b}_1 + \dots + \mathbf{b}_T \mathbf{b}_{56}$$

With parameters as explained below.

Parameter	Represents
Y	Change from baseline
b_{int}	Model intercept
b_{base}	Baseline value
b_T	Indicator for Active Treatment
b_1, \dots, b_{56}	Indicator for each timepoint, subscripts index categorical visit with 1 being the first day of treatment, and 56 being the final day of treatment.
$b_T b_1, \dots, b_T b_{56}$	Indicators allowing varying treatment differences at each timepoint

From this model estimates of treatment effect at specific visits and specifically at Week 8 difference may be obtained as follows.

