Given the amount of evidence and precedence for the 30% criterion for measures of pain severity and interference including those of the BPI, we believe a 30% score change is an appropriate threshold for clinically meaningful change in scores. For the score point CID criterion, an improvement of either 1 or 2 points on the 11-point scales could be justified. We chose to go with the more stringent 2-point CID for both measures.

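### The SAP names a hypothetical estimand, but its primary analysis scores withdrawal for lack of effectiveness as zero change, and the reason it gives does not support zero

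*SAP*

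**What the plan says.** SAP 2.9 defines the quantity of interest as the group difference in mean change from baseline to Week 8, for intensity and interference, "had subjects completed 8 weeks of follow-up and not withdrawing for lack of treatment effectiveness".

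SAP 2.9.1 reviews the options for this intercurrent event. It sets aside the composite (failure) strategy: "if the primary effectiveness endpoints are continuous changes from baseline rather than a responder analysis, another approach is necessary". It also rejects treatment policy, and it adopts the hypothetical strategy as the one that fits the estimand.

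The same section then gives its working assumption, "It is reasonably assumed that subjects who discontinue due to lack of effectiveness do not experience clinically significant improvement in pain", and from it the rule behind the main result: "a baseline carried forward approach will be used implying that subjects who discontinue due to lack of effectiveness are given a value of zero" as their change from baseline. The one sensitivity analysis named for these subjects uses their last observation before discontinuation as the Week 8 value.

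Two other places bear on this. SAP 2.6 sets the clinically important change at a 30% fall or, for the point rule, 2 points: "We chose to go with the more stringent 2-point CID for both measures". SAP 2.4 commends the MMRM because it does not fill in arbitrary values, and it names LOCF as the example of that practice.

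**The concern.** Under a hypothetical strategy, the value needed is the Week 8 change these subjects would have had if they had not withdrawn. A fixed zero for everyone with the event is a failure value placed on a continuous scale, which is in effect the composite approach that 2.9.1 has just set aside.

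Zero could still serve as an assumed counterfactual if the SAP justified it. The premise only places these subjects below a threshold of 2 points or 30%, so any smaller improvement is compatible with it. The sham arm of the previous trial improved by 1.21 points on average, so zero is not what continued follow-up would be expected to show.

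The primary result would therefore not estimate the declared quantity, and no analysis named for this event does. The zeros are not reliably conservative either: more sham than EaseVRx withdrawals for ineffectiveness can favour EaseVRx. A single fixed value also ignores the uncertainty in what it replaces.

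Finally, the event is not defined. The heading of 2.9.1 speaks of withdrawal of the subject, while its text speaks of discontinuation. Under Protocol 13.1, stopping the device does not by itself end participation, so a participant can stop and still supply a Day 56 BPI. The SAP does not say whether a zero would overwrite that score.

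**Working it through.** **Inputs.** From SAP 2.8.1, Table 2, intensity:
- EaseVRx: baseline mean 5.10, change -2.12 (SD 1.64).
- Sham: baseline mean 5.24, change -1.21 (SD 1.68).
- Subjects: 94 at baseline and 84 at Week 8 in each arm.

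From the SAP sample-size text: maximum N of 1000, 15% loss, success at p < 0.025 with the alternative that the difference is below zero, Hochberg over two endpoints. The documents give no rate of withdrawal for lack of effectiveness, so every rate below is an assumption.

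**1. The plan's own figure.** Simulating 20,000 trials at 120 per arm from the Table 2 means, SDs and correlations, with one-sided t-tests and Hochberg at 0.025, gives 97.9% power. This agrees with the stated figure of more than 95%. No subject in that calculation is set to zero.

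**2. Does missing the threshold imply zero?** Assume normal change. The mean among subjects who miss a cut c is mu + sd × phi(a)/(1 − Phi(a)), with a = (c − mu)/sd.
- Cut −2, sham: a = −0.470; −1.21 + 1.68 × 0.3572/0.6809 = **−0.33**.
- Cut −2, EaseVRx: a = 0.073; −2.12 + 1.64 × 0.3979/0.4708 = **−0.73**.
- Cut at 30% of mean baseline, sham (−1.572): **−0.09**.
- Cut at 30% of mean baseline, EaseVRx (−1.53): **−0.41**.

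None is zero, and the arms differ. Subjects who quit for ineffectiveness may differ from the average non-responder, so these values are a guide only.

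**3. Bias.** Let pi be the share of an arm with the event and m the mean change those subjects would have had. Zero-filling moves each arm mean by −pi × m, so

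bias in (EaseVRx − Sham) = pi_S × m_S − pi_T × m_T,

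where a negative value favours EaseVRx. It vanishes only when the two products are equal.

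**4. No true effect.** Per arm, n = 1000 × 0.85/2 = 425. SE = 1.66 × √(2/425) = 0.1139, where 1.66 is the mean of the two SDs. Rejection probability = Phi(−1.96 − bias/SE), for intensity alone, with the same m in both arms:

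| EaseVRx / sham rate | Bias, m = −0.3 | Rejects | Bias, m = −0.6 | Rejects |
|---|---|---|---|---|
| 2% / 4% | −0.006 | 2.8% | −0.012 | 3.2% |
| 3% / 8% | −0.015 | 3.4% | −0.030 | 4.5% |
| 2% / 10% (upper case) | −0.024 | 4.0% | −0.048 | 6.2% |
| 4% / 2% | +0.006 | 2.2% | +0.012 | 1.9% |

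For Hochberg over both endpoints, 40,000 trials were simulated per scenario with z-tests, SDs 1.66 and 1.98, correlation 0.77, and means −1.21 and −1.82 in both arms. Withdrawers' counterfactual changes (intensity, interference) were (−0.3, −0.45) or (−0.6, −0.9). Rejection rates:
- 2% / 4%: 2.8% or 3.0%.
- 3% / 8%: 3.3% or 4.5%.
- 2% / 10%: 4.0% or 6.6%.
- 5% / 5%: 2.2% or 2.3%, so no inflation.

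**5. True intensity effect of −0.91.**
- 5% / 5%, m equal to the arm means: 0.05 × (−1.21) − 0.05 × (−2.12) = +0.0455, so −0.91 becomes −0.86.
- 5% / 5%, m equal to the below-2-point means: 0.05 × (−0.329) − 0.05 × (−0.734) = +0.020, giving −0.89.
- 2% / 10%, arm means: 0.10 × (−1.21) − 0.02 × (−2.12) = −0.079, giving −0.99.
- 15% EaseVRx / 5% sham, arm means, as a stress case: 0.05 × (−1.21) − 0.15 × (−2.12) = +0.258, giving −0.65.

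The rejection rates are not adjusted for baseline, so they only approximate the MMRM.

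**The case against.** The best defence is that a hypothetical estimand always needs an assumption about unobserved values. The SAP states one, and zero is its implementation rather than a failure score. The below-30% averages of −0.09 and −0.41 are not far from zero on a 0–10 scale. This does not rescue the rule. The premise bounds the improvement and does not fix it, and the SAP gives no argument that the products pi × m are equal across arms.

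Second, other analyses exist. The Completers set drops subjects without a Week 8 score, the Per Protocol set drops low users, and LOCF inserts each subject's own last value. A reader would see some sensitivity to the zeros. None of these targets the stated estimand: the first two select on post-randomisation behaviour, and the third is another single imputation.

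Third, the inflation scenarios may be strained. They assume no effect, yet more sham subjects quitting for ineffectiveness. The only arm-level loss in the documents is equal (10 of 94, or 10.6%, from all causes in each arm). The m = −0.6 column is nearly twice the −0.33 that the sham distribution implies, and with m = −0.09 the 2% / 10% case rejects only 2.9%. This stands as a limit on the size, not on the mismatch.

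Fourth, SAP 2.4 describes the MMRM's general handling, so 2.9.1 can be read as a specific exception. SAP 2.9 concerns unavailable data, while 2.4 takes in all pain values, which suggests that an observed Day 56 score would be used. That is a fair reading. However, 2.9.1 also cites guidance that such data may be irrelevant even when it can be collected, so a clarifying sentence is still needed.

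**Conclusion.** The concern holds. The declared estimand and the primary estimator do not match, and the reason given for zero does not support it. This follows from the SAP's text and does not depend on any assumed rate.

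The numerical effect is probably small. Protocol 13.1 expects only a small share of participants to want to withdraw, for all the reasons it lists together. At modest assumed rates the one-sided error moves from 2.5% to about 3%, and equal rates under a real effect attenuate it by 0.02 to 0.05 points. Reaching 4% to 6.6% takes a five-fold imbalance towards sham. An imbalance towards EaseVRx works against the device. These sizes rest on the assumed rates, on normality, and on the previous trial's means and SDs.

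This should be fixed because it decides what the primary result means; it does not threaten the design.

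**What to change.** Before unblinding, make the estimand and the estimator agree in one of two ways:

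- **(a)** Keep the hypothetical estimand. Treat Week 8 values after withdrawal for lack of effectiveness as missing in the primary MMRM, and keep zero-change and LOCF as sensitivity analyses.
- **(b)** Keep zero-change as primary, restate the estimand as composite-type, and add the MMRM with those values missing as a sensitivity analysis.

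Under either option, state whether the event is study withdrawal or device discontinuation, and whether the rule applies at Week 8 only or at every later visit. Handle a Day 56 BPI collected after the event to match: set to missing under (a), replaced by zero under (b). Add one sensitivity analysis that uses all observed Day 56 scores.

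The cost is SAP wording and one or two extra runs, with no new data. The drawback of the MMRM run is that it relies on missing at random for the subjects where that assumption is least secure. SAP 2.4.2 already relies on it for the MMRM, and the zero-change run shows the effect of departing from it. Which run is primary is the sponsor's choice, provided the estimand wording follows it.
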